5.4. Biomarker measurement

Upon transfer of plasma aliquots from hospital site to Pockit diagnostics, a panel of plasma proteins and metabolites will be measured by Pockit diagnostics. Measurement of protein markers will be performed using commercial enzyme-linked immunosorbent assay (ELISA) kits. Plasma metabolites will be measured with commercial enzymatic assay kits. All assays will be performed according to manufacturer's instructions and compliant to ISO13485 and cGMP.

Pockit diagnostics may sub-contract an external contract research organisation (CRO) to perform biomarker measurement. In this case, blood samples will be transferred from UMMC to the designated CRO.

Interim analyses may be performed upon collection of the first 100, or 200 samples. In all these cases, transfer of collected clinical data from the hospital site to Pockit diagnostics (or designated CRO) will be required to perform the interim analysis. Results from interim analyses will evaluate the necessity to modify the study protocol or to continue sample recruitment.

6. Study population

A total of up to 400 patients are expected to be recruited in this study. In order to be eligible for study participation, subjects must meet the following inclusion and exclusion criteria at the time of consent.

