6.3. Withdrawal criteria

Patients and blood samples will be withdrawn from this study in case:

- 1) More than 60 minutes have passed from blood withdrawal to beginning of centrifugation;
- 2) Presence of haemolysis in blood plasma;
- 3) Absence of imaging results.

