6.4. Sample size estimation

The proposed intended use of the test is to rule in patients with LVO to redirect them to EVT-capable centers from a population of suspected stroke, thus we powered the study on specificity. Assuming a prevalence of 20%, a minimum specificity of 90%, a two-tailed 5% type I error rate (**a**) and 90% power (**β**), a sample size of 329 suspected stroke patients with 66 LVO cases would detect a diagnostic specificity of 95% (95%CI: 90%–100%) for each

algorithm. Accounting for 20% of data loss due to missing patient data or sample lysis, a final number of 395 patients will be required.

Sample size estimation was performed according to Chu and Cole⁸.

Prevalence of LVO/ischemic stroke will be monitored during recruitment to ensure that calculated sample size is appropriate for actual prevalence. A prevalence in the range of 10-30% LVO will be accepted. In case observed prevalence will be outside the acceptable range, sample size will be re-estimated and recruitment size adjusted accordingly.

7. Data management

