7.4. Data analysis plan

Clinical and biomarker data will be curated after clinical and technical monitoring to assure maximum validity of the data utilised to construct the algorithm. Any subject matching

criteria as defined in section "6.3 – Withdrawal criteria" will not be incorporated into the primary analysis. This data is quarantined for a separate sub-group analysis where relevant.

Data exploration

Data will be explored by generating box plots of blood biomarker concentrations (plasma or whole blood) and clinical data, according to stroke subtypes. Concentrations of blood biomarkers and clinical data (where applicable) may undergo pre-processing and/or transformations to ensure statistical assumptions are met prior to analysis. Akaike information criterion (AIC) will be used to assess the need of transformations.

Whole blood biomarker concentrations

Plasma concentration of individual biomarkers will be adjusted based on whole bloodto-plasma (WBP) ratios, in order to obtain whole blood biomarker concentrations. Values of biomarker concentrations (plasma or whole blood) will be reported with corresponding values of standard error of the mean (s.e.m.).

Covariate analysis

Association between clinical variables and concentration of individual blood biomarkers will be assessed. A linear regression model between biomarker concentration (as the outcome) and key clinical covariates will be generated.

Biomarker kinetics

To assess the effect of biomarker kinetics on diagnostic performance, patient population will be divided into 3-hour and 6-hour bins based on their stroke onset to blood collection time and multivariate logistic regression will be performed on each population bin separately. Alternatively, the distribution of stroke onset to blood collection times will be assessed and the population will be divided into quartiles or halves, and compared. Results from this analysis will be compared to results obtained on the whole population and will inform if the test will be limited to a specific time window from stroke onset.

Diagnostic performance

Values of diagnostic accuracy, sensitivity, specificity, positive and negative likelihood ratios will be calculated and reported with confidence intervals. ROC curve will be drawn and the area under the ROC curve will be reported with confidence intervals. Confidence intervals will be estimated via 2000 bootstrapped replicates.

Biomarker diagnostic thresholds

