Thresholds of individual biomarkers already established by Pockit diagnostics will be validated for their diagnostic performance. If the accuracy achieved by the model is below acceptable levels (specificity <90% and/or sensitivity<60%) we will aim to refine the model using data from our 395 patient cohort.

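### Section 6.4 allows for 20% loss by multiplying 329 by 1.2; a 20% loss from the resulting 395 leaves about 316 evaluable patients, 13 short of 329 (small effect)

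*Combined protocol and SAP*

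**What the plan says.** Section 6.4 powers the study on specificity: LVO prevalence 20%, minimum specificity 90%, expected specificity 95%, a two-tailed 5% type I error rate and 90% power. The result is that "a sample size of 329 suspected stroke patients with 66 LVO cases would detect a diagnostic specificity of 95" per cent. The loss allowance follows directly: "Accounting for 20% of data loss due to missing patient data or sample lysis, a final number of 395 patients will be required".

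Three other places bear on how these numbers are read:

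- Section 6 (Study population) sets the scale of recruitment: "A total of up to 400 patients are expected to be recruited in this study".
- Section 6.3 lists the grounds for removal (over 60 minutes to centrifugation, haemolysis, no imaging results) under the words "Patients and blood samples will be withdrawn from this study in case". Section 7.4 says that data from such subjects "will not be incorporated into the primary analysis".
- Section 7.4, under the diagnostic thresholds, plans if performance is inadequate to "refine the model using data from our 395 patient cohort".

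**The concern.** The 329 is the number needed in the analysis, since specificity can be estimated only from patients with a usable sample, usable data and a reference diagnosis. The 395 is the number to enrol so that 329 remain. For a loss of 20% of those enrolled, the required enrolment is the evaluable number divided by 0.8. The plan multiplies it by 1.2, which always falls short.

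On the ordinary reading, then, 329, 20% and 395 cannot all hold. The power is plainly attached to 329, but the stated enrolment does not deliver 329 at the stated loss. At stake are a modest loss of power and precision for specificity, and a sample size statement that does not add up. Section 6.4 also provides for re-estimating the sample size if LVO prevalence falls outside 10–30%, and the same inflation step could be carried into that recalculation.

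**Working it through.** **Inputs.** Section 6.4: 329 patients, 66 with LVO, hence 329 − 66 = 263 without; loss 20%; enrolment 395; prevalence 20%; specificity 0.95 against a minimum of 0.90. Section 6: up to 400 patients.

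**1. Reproduce the plan's figure.** 329 × (1 + 0.20) = 394.8, rounded up to 395. This is how the plan's number arises.

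**2. Apply the stated loss to the stated enrolment.**

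| Enrolled | Evaluable at 20% loss | Short of 329 | Largest loss that still leaves 329 |
|---|---|---|---|
| 395 | 395 × 0.8 = 316 | 13 | 1 − 329/395 = 16.7% |
| 400 | 400 × 0.8 = 320 | 9 | 1 − 329/400 = 17.75% |

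At 20% prevalence, 316 evaluable patients are 252.8 ≈ 253 non-LVO and 63.2 ≈ 63 LVO, against 263 and 66 in the plan: about 10 and 3 fewer.

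**3. Enrolment consistent with 329 evaluable at 20% loss.** 329/(1 − 0.20) = 411.25, so 412. That is 17 more than 395 and 12 above 400.

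**4. Effect on power.** The test is an exact binomial test of specificity 0.90 against 0.95 in non-LVO patients. It rejects when the number correctly classified is at least the smallest r with P(X ≥ r | n, 0.90) ≤ α. Power is P(X ≥ r | n, 0.95).

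At one-sided α = 5%, 263 is the smallest non-LVO count from which power stays at or above 90%, and 263/0.8 = 328.75, which rounds up to 329. That reproduces the plan's base figure. The two-tailed 5% that the plan states corresponds to a 2.5% tail, so both are shown.

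Exact power moves up and down with n because r is a whole number. At one-sided 5%, for example, it is 92.9% at n = 263, 91.4% at 253 and 87.5% at 250. A single count is therefore a poor guide. The non-LVO count is in any case random, so power is averaged over n ~ Binomial(N evaluable, 0.8):

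| Evaluable N | One-sided 5% | 2.5% tail |
|---|---|---|
| 329 | 91.1% | 84.2% |
| 320 | 90.4% | 83.0% |
| 316 | 90.0% | 82.4% |
| Change, 329 to 316 | −1.1 points | −1.8 points |

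Only the last row measures this slip. The 2.5% tail column lies below 90% even at 329 evaluable, because of the choice of α, which is a separate question.

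**5. Effect on precision.** The Wald 95% half-width at a specificity of 95% is 1.96 × √(0.95 × 0.05/n): 2.63 percentage points at n = 263 and 2.69 at n = 253.

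**The case against.** The strongest reply is that section 6.4 does not say what the 20% is a percentage of. If it means an allowance equal to 20% of the required 329, that is 66 patients, and 395 − 66 = 329, so the sentence is consistent. This reading is possible but not stated, and a data loss rate is more naturally a share of the data collected. On this reading, 395 covers a loss of only 16.7% of those enrolled, which the text should then say. The sentence needs changing either way.

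A second reply is that the effect is negligible, and much of this stands. At one-sided 5%, average power with 316 evaluable is still 90.0%. The accepted prevalence range of 10–30% alone moves the non-LVO count at 329 evaluable between about 296 (329 × 0.9) and 230 (329 × 0.7), far more than the 10 patients at issue. This limits the weight of the point but does not make the figures agree. The re-estimation rule in section 6.4 does not cover the shortfall, because it is triggered by prevalence and not by data loss.

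Third, the removal criteria in section 6.3 and the losses named in section 6.4 overlap without being identical: late centrifugation is not named in the 20%, and missing data other than imaging is not a removal criterion. That is correct. Section 7.4 shows that removed patients reduce the analysed number; it does not show that exactly 20% will be lost.

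**Conclusion.** The point holds, and it is minor. With 20% of enrolled patients lost, 395 enrolled gives 316 evaluable, 13 fewer than the 329 to which the power is attached; 400 enrolled gives 320. The cost is about 1 to 2 percentage points of power and about 0.05 points of confidence interval half-width. No endpoint, analysis or conclusion of the plan changes.

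The shortfall assumes that the 20% is a share of those enrolled. The power figures further assume 20% LVO prevalence, a true specificity of 95%, and an exact binomial test against 90%. The inflation slip does not depend on how 329 was derived or on whether the test is one- or two-tailed. The phrase "refine the model using data from our 395 patient cohort" in section 7.4 is loose about enrolled versus evaluable patients; it is not a second error.

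**What to change.** Restate the loss sentence in section 6.4, saying what the 20% is a percentage of, in one of two ways:

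- (a) 395 enrolled gives about 316 evaluable patients (about 253 non-LVO and 63 LVO) at 20% loss, followed by the power for that number at the α the sponsor intends; or
- (b) 395 enrolled gives 329 evaluable patients provided that loss is at most 16.7% of those enrolled.

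The figure of 412 can be noted for information; extra enrolment is not required for an effect of this size. Any re-estimation of the sample size during recruitment should divide by one minus the loss rate.

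Optionally, make clear in section 7.4 that the 395 are enrolled patients and that the analysis uses the evaluable ones.

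The cost is wording only: one sentence in section 6.4 and, if wanted, one phrase in section 7.4.

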7.1. Data sources and collected data

Clinical data

Different types of clinical data will be collected in this study:

- 1) *Final diagnosis*: LVO ischemic stroke, non-LVO ischemic stroke, hemorrhagic stroke, stroke mimic
- 2) Demographics: Age, sex, smoking, etc
- 3) Specific Clinical data: atrial fibrillation, systolic/diastolic blood pressure, hypertension.
- 4) Stroke scaling score:
 - a. NIHSS score and individual NIHSS items used to calculate the score, as collected at the time of patient admission to ED.
 - b. FAST-ED score collected by ambulance paramedics;
 - c. FAST score collected by ambulance paramedics;
 - d. Any other stroke severity scale collected pre-hospitally (e.g. EMSA, RACE).
- 5) **Stroke onset to blood collection time (OBT)**. Time from presumed onset of stroke (as interpreted by local stroke physician) to blood collection will be recorded to evaluate kinetic dynamics of blood biomarkers.
- 6) Whole blood-to-plasma ratio (WBP). The volume of whole blood drawn from patient and the volume of plasma resulting after centrifugation will be collected. This information is fundamental because different subjects have different WBPs, and analysis of plasma samples only could create a bias. Recording WBPs from each patient will allow to keep track of the real concentration of biomarkers in whole blood and normalise patients based on their WBPs.

Biomarker data

After collection, blood samples will be stored at -80°C until shipment to Pockit diagnostics. Data on absolute concentrations of blood biomarkers will be obtained using standard procedures (see section 5.4).

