The aim of the TIME study is to validate the clinical diagnostic performance of previously defined diagnostic thresholds of Pockit diagnostics' algorithm. Results of this study will direct the development of a diagnostic test for identifying LVO patients in the field, directing them to EVT centre, ultimately enabling faster treatment, and improving patient outcomes.

3. Aim of the study

The primary aim of this study is to validate the clinical diagnostic performance of previously defined cut-off points on the plasma concentration of D-dimer and GFAP, combined with stroke severity scales (FAST-ED, FAST, EMSA, RACE, C-STAT).

The secondary aim of the study is to optimise the cut-off points of the diagnostic algorithm for LVO detection, in a larger and inter-racial patient population.

4. Study endpoints

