5.2. Sample collection and processing

One 5 mL sample of venous blood will be collected from each consented patient. Blood will be collected using standard procedure. Briefly, blood samples from a single blood draw will be collected into tubes containing sodium EDTA and immediately placed on ice. Blood samples will be processed immediately or within 30 minutes from withdrawal. Blood samples collected into EDTA tubes will be centrifuged at 2000 g for 15 minutes at 4°C. Plasma will be divided into 3 aliquots of ~1 mL each and all plasma aliquots will be frozen at -80° C. Plasma aliquots will be stored at hospital site until transfer to Pockit diagnostics.

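### The whole-blood adjustment rests on tube volumes with no stated reading method and no haematocrit check, so handling error enters every whole-blood value and could, if volumes are read coarsely, match the variation it should correct

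*Combined protocol and SAP*

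**What the plan says.** All references are to the combined protocol and SAP.

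- **Section 5.2 (sample collection):** "One 5 mL sample of venous blood will be collected from each consented patient". The tube is "centrifuged at 2000 g for 15 minutes", and then "Plasma will be divided into 3 aliquots of ~1 mL each". The section does not say how close to the cell layer plasma is drawn, or how its volume is read.
- **Section 7.1, item 6 (ratio):** "The volume of whole blood drawn from patient and the volume of plasma resulting after centrifugation will be collected". The reason given is that "different subjects have different WBPs, and analysis of plasma samples only could create a bias".
- **Section 7.4 (whole-blood concentrations):** "Plasma concentration of individual biomarkers will be adjusted based on whole bloodto-plasma (WBP) ratios". The next sentence leaves the scale open: "Values of biomarker concentrations (plasma or whole blood) will be reported". No formula is given.
- **Section 3 (primary aim):** the study is to validate "previously defined cut-off points on the plasma concentration of D-dimer and GFAP".
- **Haematocrit:** the clinical data listed in 7.1 do not include it. Section 5.1 mentions that blood is taken for laboratory work as part of usual care, but not which tests are run.

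**The concern.** The ratio is there to take out differences between patients in how much of their blood is plasma. The whole-blood value is a product of two measurements, so a proportional error in the plasma fraction becomes the same proportional error in the result. If the fraction comes from a volume read at the bench, anything that makes that volume vary for reasons other than the patient is added to every whole-blood value: plasma left above the cells, coarse reading, or entering a nominal figure.

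The plan sets no reading precision, no rule for the residual and no independent check. The study is multi-centre and samples are processed on site, so differences in habit can appear as differences between sites. Once plasma has been aliquoted and frozen, the volume that was in the tube cannot be measured again. At stake is a quantity that 7.1 itself calls fundamental.

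**Working it through.** The plan states no figure for handling error or for the spread of the ratio, so there is nothing of its own to reproduce. Only the 5 mL draw and the three aliquots of about 1 mL come from the documents. The haematocrit range, spreads, residuals and reading steps below are assumptions.

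**1. Model.** Since 7.4 gives no formula, take whole-blood concentration = plasma concentration × plasma fraction, with fraction = plasma volume / blood volume.

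**2. Nominal yield.** 3 × 1 mL from 5 mL gives 3/5 = 0.60. Plasma present is 5 × (1 − haematocrit):

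| Haematocrit | True fraction | Plasma in tube (mL) |
|---|---|---|
| 0.35 | 0.65 | 3.25 |
| 0.40 | 0.60 | 3.00 |
| 0.45 | 0.55 | 2.75 |
| 0.50 | 0.50 | 2.50 |

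A full 3 mL is available only at a haematocrit of 0.40 or below, and at 0.40 only with nothing left behind. The true fraction spans 0.575 ± 0.075, or ±13%.

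**3. Break-even.** Let s be the between-patient SD of the true fraction and h the SD of the handling error in the fraction, with h = (volume-error SD)/5 mL. Adjusting removes variance s² and adds h², so nothing is gained once h = s, that is, at a volume-error SD of 5 × s:

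| Assumed s | Break-even volume-error SD (mL) |
|---|---|
| 0.03 | 0.15 |
| 0.04 | 0.20 |
| 0.05 | 0.25 |
| 0.06 | 0.30 |

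At s = 0.04, the share of variance in the measured ratio that is truly between patients, s²/(s² + h²), is 0.94, 0.80, 0.50 and 0.31 for volume-error SDs of 0.05, 0.10, 0.20 and 0.30 mL. Over volume-error SDs of 0.05–0.40 mL and s of 0.03–0.06, h/s runs from 0.01/0.06 = 0.17 to 0.08/0.03 = 2.67.

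**4. Reading step alone.** Rounding SD = step/√12:
- 0.1 mL: 0.03 mL, far below break-even.
- 0.5 mL: 0.14 mL, just under the lowest break-even value.
- 1 mL (counting aliquots): 0.29 mL, above break-even for s up to 0.05. The formula is crude for so coarse a step. The practical limit is that every patient is entered as 3 mL, so the ratio is 0.60 for all and corrects nothing. It is then 0.60/0.55 = 1.09 (9% high), 0.60/0.50 = 1.20 (20% high) or 0.60/0.65 = 0.92 (8% low).

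**5. Fixed residual of 0.4 mL.** Measured fractions are 0.57, 0.52, 0.47 and 0.42, which is 12.3%, 13.3%, 14.5% and 16.0% low. The range is 0.15, the same as the true range. Measured/true moves only from 0.877 to 0.840, about ±2% between patients. The ratio of the extremes becomes 0.57/0.42 = 1.36 instead of 0.65/0.50 = 1.30, a slight over-correction.

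**6. Variable residual of 0.2–0.6 mL at haematocrit 0.45.** Measured fractions run from 0.51 to 0.43 against a true 0.55 (−7.3% to −21.8%). Around their midpoint this is 0.47 ± 0.04, or ±8.5%, against the ±13% in step 2.

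**The case against.** A reader might infer that the handling error is as large as the between-patient difference. The documents do not support that. They give no error size, and step 3 allows anything from well below to well above it. The 12–16% in step 5 looks comparable with ±13%, but it is mostly a shift common to all patients, whereas ±13% is a spread between them. The variable residual in step 6 also falls short of the assumed signal.

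Three further points count against a strong reading:

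- The volume to be recorded may be the layer read in the spun tube, in which case plasma left above the cells does not enter the ratio. That pipetted plasma is meant is an inference.
- The aliquots are only approximately 1 mL. Three of 0.9 mL make 2.7 mL, which fits within the 2.75 mL present at haematocrit 0.45. Plasma volume is also a separate item in 7.1, not defined as the aliquot total, so nominal recording is a risk and not something the plan instructs.
- An under-filled tube entered as 5 mL (4.5 mL drawn would put the ratio 10% low) presumes a wrong entry, since 7.1 asks for the volume drawn.

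A reader might also infer damage to the primary sensitivity and specificity. The primary cut-offs are on plasma, and without cut-off values or biomarker distributions no such effect can be computed. It could arise only if whole-blood values were fed into the algorithm, which the open wording in 7.4 does not rule out.

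These objections remove any claim to a known size. They leave the gap itself: neither reading of the recorded volume is specified, no precision is set, and nothing checks it.

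**Conclusion.** The concern holds as a measurement gap of conditional size. The adjustment in 7.1 and 7.4 depends on a bench volume with no reading method and no haematocrit check, so variable recovery or coarse reading puts error into every whole-blood value. If the between-patient SD of the plasma fraction is 0.03–0.06, that error equals the variation it should correct at a volume-error SD of 0.15–0.30 mL. Careful reading to 0.1 mL keeps the rounding part far below this; counting whole aliquots does not. A constant residual mainly lowers all values and distorts the between-patient correction only slightly, although it would matter against a fixed whole-blood cut-off. All spreads and residuals are assumed. The effect falls on the whole-blood results, and none on the primary measures is shown.

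**What to change.** 1. **Sections 7.1 (item 6) and 7.4:** define the plasma fraction as 1 − haematocrit, taken from the admission blood count where one exists, and record the haematocrit in the CRF. That a blood count is among the routine tests is an assumption to confirm with sites. State the conversion formula in 7.4.
2. **Fallback:** keep the tube volumes for patients without a haematocrit and flag those values. Read the plasma layer in the spun tube before pipetting, and use the volume actually drawn.
3. **Section 5.2:** change the instruction to up to 3 aliquots of up to about 1 mL, so that sites are not led to record a nominal 3 mL.

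The cost is one CRF field and some wording. The downside is that patients without a haematocrit rely on the less precise fallback; the documents do not allow their number to be estimated.
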